### 3.2 Short Term Endpoints

The primary short-term efficacy endpoint regarding the cell product and its delivery procedure is:

Change in right ventricular cardiac function at 3 months post-Stage II surgery compared to baseline, measured by *apical fractional area change, circumferential strain, and longitudinal strain on echocardiogram*.

Secondary short-term efficacy and safety endpoints in order of their relevance and importance in this clinical study are:

- 1) Change in cardiac function between baseline and hospital discharge for Stage II surgery, measured by echocardiogram.
- 2) Cumulative days of hospitalization per patient at 1 and 3-months post Stage II surgery.
- 3) Change in weight, heart rate, and oxygen saturation at 3-months post Stage II surgery compared to baseline.

Additional variables may be assessed in an exploratory manner.

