### 3.3 Long Term Endpoints

The primary long-term efficacy endpoint regarding the cell product and its delivery procedure is:

Change in right ventricular cardiac function at 12 months post-Stage II surgery compared to baseline, measured by echocardiogram.

Secondary long-term efficacy safety endpoints in their order of relevance and importance in this clinical study are:

- 1) Change in weight every 6 months post-Stage II surgery compared to baseline.
- 2) Change in heart failure medication taken every 6 months post-Stage II surgery compared to baseline.
- 3) Change in arrhythmia medication taken every 6 months post-Stage II surgery compared to baseline.

- 4) Success of subject being scheduled for Stage III surgical repair.
- 5) Time (days) until listed for cardiac transplantation, or death following the 6-month follow-up.
- 6) Change in right ventricular function at Stage III surgery pre-op work-up compared to baseline, obtained by echocardiogram, cardiac MRI, and cardiac catheterization.

Additional variables may be assessed in an exploratory manner.

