#### **4.6 Discontinuation and Withdrawal Subjects**

A subject will be considered a lost to follow-up subject after three documented attempts (the third attempt will be a certified letter) have resulted in failure to contact the parent(s) and/or legal guardian(s).

For the treatment arm, subjects will be discontinued from the study if there is a compromise to the cell product (see Section 5.4.2) following subject enrollment.

Parent(s) and/or legal guardian(s) may decide to withdraw their child from the study at any time during participation in the study. If the parent(s) and/or legal guardian(s) request that their child be withdrawn from the study, the Sponsor will utilize data collected up to that time point but will discontinue future study follow-up assessments. Survival status data will be collected through search of public records by the enrolling site. If a subject has discontinued from active participation but not from the study, standard of care echocardiograms, MRIs, cardiac catheterizations, ECGs, laboratory tests, weight/vitals, and new or worsening conditions that are normally collected for this study will be collected from the subject's medical records, if the parent(s) and/or legal guardian(s) have previously consented to this additional collection of standards of care data. This data is important to ensure there are no safety issues and to monitor for evidence of efficacy in subjects that have decided to withdraw from active participation in the study. Withdrawn subjects and subjects that discontinue from active participation but not from the study will be documented in the applicable eCRF. Documentation must be provided in the subject study chart for any study withdrawal or discontinuation.

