#### Lost to follow up

Follow up times for subjects who are in study at the time of analysis will be censored in time-to event analysis, as with time until listing for cardiac transplant. Since the outcome regarding time to listing includes death as part of a compound outcome, there will be no censoring for death. In case of lost to follow up before time of analysis subjects will be censored, unless the investigators feel the subject could have been indicated for transplant in which case they will be included as such in the analysis.

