## 9 DATA HANDLING AND RECORD KEEPING

### 9.1 Confidentiality

Information about study subjects will be kept confidential and managed according to the requirements of the Health Insurance Portability and Accountability Act of 1996 (HIPAA). Those regulations require a signed subject authorization informing the subject of the following:

- What protected health information (PHI) will be collected from subjects in this study
- Who will have access to that information and why
- Who will use or disclose that information
- The rights of a research subject to revoke their authorization for use of their PHI

If a subject revokes authorization to collect or use PHI, the site investigator, by regulation, retains the ability to use all information collected prior to the revocation of subject authorization. For subjects that have revoked authorization to collect or use PHI, attempts should be made to obtain permission to collect at least vital status (long term survival status that the subject is alive) at the end of their scheduled study period.

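### The records kept after a child stops active participation (4.6) name no medications or transplant listing, and listing-or-death is ascertained differently by exit route

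*Combined protocol and SAP*

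**What the plan says.** Section 4.6 describes three ways out of active follow-up.

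- **Full withdrawal.** Data up to that point are used and study assessments stop. The next sentence reads: "Survival status data will be collected through search of public records by the enrolling site".
- **Stopping active participation while remaining in the study.** The site takes from the medical record "standard of care echocardiograms, MRIs, cardiac catheterizations, ECGs, laboratory tests, weight/vitals, and new or worsening conditions that are normally collected for this study", provided the parents "have previously consented to this additional collection of standards of care data". The stated reasons are safety and evidence of efficacy.
- **Loss to follow-up.** This is declared after three documented failed contacts. No later data collection is described.

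The endpoints that bear on this list are short-term secondary 2, "Cumulative days of hospitalization per patient at 1 and 3-months post Stage II surgery" (3.2), and four long-term secondaries in 3.3: number 2, "Change in heart failure medication taken every 6 months post-Stage II surgery compared to baseline"; number 3, the same for arrhythmia medication; number 4, "Success of subject being scheduled for Stage III surgical repair"; and number 5, time to transplant listing or death after the 6-month follow-up.

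In the analysis plan, 7.3 says: "In case of lost to follow up before time of analysis subjects will be censored". It adds an exception: where the investigators feel that a lost child could have been indicated for transplant, the child is counted that way. Other missing values are carried forward where appropriate and otherwise left missing.

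**The concern.** The list in 4.6 exists partly to preserve efficacy information, yet it omits items that several secondary endpoints need. It looks like an oversight. For children still followed by phone, 6.3.3 has sites use medical records for medication changes, adverse events and weight; the 4.6 list keeps counterparts of the last two and omits the first. Likewise 6.3.4 takes the Stage III work-up date from the record, but 4.6 does not name that date.

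Two consequences follow. First, drug status after exit is not recorded. If last observation carried forward were then applied, the last recorded status would stand at every later 6-month point and read as no change. Second, the listing-or-death composite would mean different things for different children: both components while active, mainly death after exit, and possibly neither after loss to follow-up. Families know their child's arm and treatment was not randomized, so the mix of exit routes could differ between arms and produce a difference that is not a treatment effect.

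**Working it through.** No figure in the plan quantifies this point, so the check sets the 4.6 list against the endpoints item by item.

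| Secondary endpoint | Item in the 4.6 list that carries it | After active participation stops |
|---|---|---|
| Short-term 1, cardiac function at discharge | Echocardiogram | Covered |
| Short-term 2, hospital days at 1 and 3 months | None for day counts; event-driven admissions are serious adverse events (8.1.2, 8.2) and can enter as new or worsening conditions | Affected only if exit is before 3 months |
| Short-term 3, weight, heart rate, saturation | Weight/vitals | Covered |
| Long-term 1, weight | Weight/vitals | Covered |
| Long-term 2, heart failure medication | None | Not captured |
| Long-term 3, arrhythmia medication | None | Not captured |
| Long-term 4, scheduled for Stage III | None directly; work-up echocardiogram or catheterization | Proxy only |
| Long-term 5, listing or death | Death can enter as a fatal condition; listing has no item | Listing not captured |
| Long-term 6, function at Stage III work-up | Echocardiogram, MRI, catheterization | Covered |

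Of the six long-term secondaries, two are not captured (2 and 3), one loses a component (5), one rests on a proxy (4) and two are covered (1 and 6). Of the three short-term secondaries, one is affected, and only for early exits. Section 4.7 does not rescue endpoints 2 and 3 through adverse events: it records the condition behind a medication change, not the drug status.

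For the composite, by exit route:

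| Route | Death | Listing date |
|---|---|---|
| Inactive, still in study | From records if consented; whether the survival search applies is not stated | Not listed |
| Withdrawn | Public-records search | Not listed |
| Lost to follow-up | Nothing stated | Nothing stated; 7.3 censors, with the investigator-opinion exception |

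**Size.** The attrition figures in 7.1 reproduce. With a two-sided t-test, alpha 0.05 and 80% power, 50 per arm detects 0.566 (stated 0.57), and 50 × (1 − 0.40) = 30 per arm detects 0.736 (stated 0.74). They concern baseline and 3-month cardiac function, so they do not size this point.

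To show only how uneven capture acts, take Stage III scheduling. Assume the same true proportion p in both arms, an unrecorded fraction u in each, and unrecorded children counted as not scheduled (the plan does not say how they would be counted). Observed proportion = p × (1 − u), so the false difference = p × (u₂ − u₁). Section 1.1 cites about 70% reaching Fontan circulation by age 5; p = 0.70 is borrowed from it, and the u values are assumed.

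- u equal in both arms: 0.70 × 0 = 0.
- u = 5% versus 20%: 0.70 × 0.95 = 66.5% versus 0.70 × 0.80 = 56.0%, a false difference of 10.5 points.
- u = 10% versus 30%: 0.70 × 0.90 = 63% versus 0.70 × 0.70 = 49%, a false difference of 14 points.

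The work-up proxy should make u smaller for this endpoint. Medication and listing have no such proxy.

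**The case against.** The strongest reply is that much of the information has another route. Deaths and event-driven admissions can enter as new or worsening conditions. The Stage III work-up comes from the medical record in any case. Hospital days are counted only to 3 months, and data before exit are kept. Inactive children are still in the study, and 4.7 records medication changes throughout participation, so a site might go on recording them. Section 6 does not itemize transplant listing or hospital days even for active children, so part of the gap is general rather than specific to 4.6.

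Most of this stands, and it limits the point. A reader might infer that five secondary endpoints are lost after exit; the table does not support that. On medication, 4.6 is the provision written for this situation and its list leaves medication out. Sites could read the two sections differently, which is itself uneven capture. No alternative route supplies a listing date.

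Four other readings go further than the text:

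- *Deaths are searched only for withdrawn children.* The order of the sentences suggests it, but the text does not restrict the search. What stands is that its scope is unclear and that nothing is stated for lost children.
- *Up to 20 of 50 children per arm will leave.* The 40% in 7.1 is a scenario for 3-month cardiac data that mixes attrition with incomplete data. It is not a forecast of leavers over four years.
- *Section 9.1 contradicts 4.6.* Under 9.1, "attempts should be made to obtain permission to collect at least vital status" applies when authorization to use health information is revoked; 4.6 concerns withdrawal from the study. The triggers differ.
- *Controls will leave more often, or event rates will be inflated.* Section 1.4 reports difficulty recruiting untreated children, not retaining them, and says visits were reduced in response. Inflation arises only if search deaths are counted while surviving leavers stay censored at exit, and the plan does not say that it will do this.

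**Conclusion.** The point holds as a gap in data collection for secondary endpoints. Followed as written, 4.6 stops heart failure medication, arrhythmia medication and transplant listing at exit from active participation. Stage III scheduling is left to a proxy, and hospital days are at risk only for exits before 3 months. Ascertainment of listing-or-death varies by exit route, and for lost children 7.3 puts an investigator's opinion where a recorded date should be.

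The size is unknown because the documents give no rate for any exit route. Bias between arms also requires the rate or mix of exits to differ by arm, which is plausible in an open-label, non-randomized study but is not shown. The 10.5- and 14-point figures rest on assumed rates and show the mechanism only. The change is worth making because it is cheap and because data not collected at the time may be hard to recover.

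**What to change.** **In 4.6**, add to the record-based list: heart failure and arrhythmia medication at each 6-month point; date of transplant listing; date Stage III is scheduled or worked up; and admission and discharge dates to 3 months. State that the survival search covers withdrawn, inactive and lost children alike. State that chart collection, where consent allows, covers inactive and lost children; withdrawn children would have the survival search only. Itemizing listing and hospital dates in section 6 as well would close the same gap for active children.

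**In 7.3**, censor the composite at the last date on which both listing and survival status are known. Count deaths found by record search only if surviving leavers' time runs to the same search date. Replace the investigator-opinion exception for lost children with a recorded listing date.

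**Cost.** Wording changes, a few more chart fields, modest abstraction time at sites, some requests for outside records, and a consent line. That line may not cover children already enrolled; the consent form was not available to check. No visits or procedures are added.

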#### **4.7 Prior and Concomitant Therapy**

Concomitant medical therapies required for the medical management of HLHS or HLHS variants are expected. Concomitant therapies may include additional surgery, devices, and complex pharmacological management. All medically necessary options are permitted. However, concomitant research studies that are not standard medical care are not permitted during participation in this study, including the follow-up period. These restrictions include any pharmacological-based studies or treatment protocol where a study agent is administered to the subject, including radiation exposure that is not clinically necessary such as x-rays or CT scans. These restrictions exclude studies that are minimally invasive diagnostics and non-interventional observational studies that require the collection of blood, tissue, or non-radiation-based imaging such as echocardiography.

Medical history and concomitant medications will be recorded on a concomitant medication log and on the applicable eCRFs starting at the time of consent through hospital admission for Stage II surgery. Changes in concomitant medications will also be recorded on the concomitant medication log and applicable eCRFs throughout the subject's participation in the study starting at the time of hospital discharge following Stage II surgery. Medication changes will not be recorded in the eCRFs (and are not required on the concomitant medication log) for the Stage II surgery and post-operative hospital stay or for any other surgery, hospitalization, or procedure that a subject undergoes. If change(s) in medication(s) are a result of new or worsening condition(s) that occur after the time of enrollment, the new or worsening condition(s) will be recorded as adverse events per Section 8 of this protocol.

## 5 STUDY DRUG (TREATMENT ARM ONLY)

### 5.1 Description of Study Drug

The autologous cell-based product is collected under the UCB Collection protocol. The autologous product is manufactured at ReGen Theranostics, Inc. (Rochester, MN) according to the procedures described in IND 15343.

UCB is collected at birth and shipped to ReGen Theranostics, Inc for manufacturing. The UCB mononuclear cells (MNC) are isolated from the cord blood and frozen in cryovials containing approximately 1.5 mL of cell product, with a target concentration of 10-30 million total nucleated cells (TNC) per mL. The UCB-MNC product is tested for sterility and endotoxin and is characterized for TNC concentration and mononuclear cell content as described in IND 15343. Test results are reviewed against the pre-specified release criteria, and products that meet all release criteria are made available for distribution. Non-conforming products (products that don't meet pre-specified release criteria or have documented quality issues) are individually reviewed by the Sponsor to determine the risk of using product in this study. Non-conforming products can only be made available for distribution only if the risk is deemed acceptable by the Sponsor and documentation is sent to the site investigator(s) prior to enrolling the patient in this study to notify the investigator(s) of the specific details.

### 5.2 Packaging and Storage

The product will be labeled according to manufacturer's procedures at the time of processing. It will be stored under GMP conditions at the manufacturing facility until it is transported by the Sponsor or Sponsor delegate to the site. There is no storage of the product at the investigational site.

### 5.3 Treatment Regimen/Dose

Subjects in the treatment arm of this study will receive a single treatment with a target dose of 1-3 million TNC per kilogram of body weight of the UCB-MNC product. The product, mononuclear cells (MNC) derived from umbilical cord blood (UCB) at a concentration of 10-30 million TNC per mL, will be administered via direct epicardial injections of 0.1 mL per injection. To achieve the target dose, subjects will receive one injection of 0.1 mL of autologous product for every 1 kg of bodyweight. The number of injections will be determined prior to the start of the surgical case and will be based on the body weight (kg) of the subject obtained at the pre-operative baseline visit, rounded down to the nearest integer. (For example, a 6.9 kg child would receive six 0.1mL injections.)

### 5.4 Product Request, Administration, Accountability, and Return/Destruction

#### 5.4.1 Product Request

After consent of the subject, the site investigator will request the investigational product for the designated subject from the Sponsor. The Sponsor will review the request and confirm the subject identity prior to submitting a request for distribution to the manufacturer. Product will be

transported in a dry shipper to the investigational site prior to cell delivery by the Sponsor or Sponsor delegate.

#### **5.4.2 Product Administration**

Prior to thawing the cells, the identity of both the product and the subject will be confirmed by the study team at the time of enrollment. Following enrollment, trained and delegated team member(s) will thaw the investigational product within the surgical suite. Once thawed, the pre-calculated volume (see Section 5.3) of UCB-MNC product will be loaded into a 1 mL syringe fitted with a 27-gauge butterfly needle and handed off to a site investigator for the cell delivery procedure. The product delivery into the heart tissue should begin within 30 minutes from the beginning of product thawing.

The cell delivery will be performed with injections directly through the epicardial surface of the myocardium, within the free wall of the right ventricle, avoiding epicardial vessels.

Approximately 0.1mL will be delivered per injection site, over 5-10 seconds, followed by 20 seconds of rest prior to needle withdrawal to maximize cell retention within the myocardium. Direct visualization will ensure the cell-based product is entering the myocardial wall and not entering into the ventricular lumen or coronary vessels or being displaced backwards through the injection site upon removal of the needle. The injection sites will be spaced approximately 1 cm apart from each other across the free wall of the right ventricle. Injection sites will be documented on a diagram to record the approximate location of injection sites relative to the coronary vasculature.

Injections will be halted upon complications such as excessive bleeding, ventricular fibrillation, sustained arrhythmias, low blood pressure requiring pharmacological support, or any other concerns of atypical physiology from anyone on the surgical team; the event(s) will be recorded as adverse event(s) on the applicable eCRF. Total volume delivered will be recorded for all partial (less than the planned cell delivery volume) and complete cell deliveries. If a partial cell delivery has occurred, subjects will continue to be followed as planned according to this protocol. Partial cell deliveries along with the specific rationale will be documented on the applicable eCRF but are not considered to be a protocol deviation.

The investigational product will NOT be used if there is any significant exposure to an unsterile field or potential compromise to the integrity of the cells, the container leaking, a failure to maintain the cells as a frozen stock prior to intentional thawing or greater than 30 minutes from the time product is started to be thawed to the beginning of injections. If a redundant back-up vial is not available in the surgical suite to replace the compromised vial of cells, then the cell delivery procedure will be cancelled.

The Sponsor and the site investigator (cardiac surgeon) performing the cell delivery procedure will be notified immediately of any discrepancies, damage or unusable product that is received prior to commencing the delivery of cells.

#### **5.4.3 Product Accountability**

Product accountability will be maintained by site personnel and will include documentation of investigational product receipt, administration of the product, and final product disposition. Any discrepancies in product accountability documentation will be investigated and documented. Additional details of the cell delivery procedure, such as the actual product volume and number of injection sites will also be recorded and entered into the applicable eCRF and within the subject's study file.

#### **5.4.4 Return or Destruction of Study Product**

Any remaining thawed product will be destroyed or discarded on site per hospital procedures. The final disposition of all unused product will be documented.

Frozen product, which remains under the continuous custody of Sponsor-delegated team member(s), may be returned to the manufacturer by the Sponsor's delegate(s).

